| | 
 ▪ C ▪ Other ○ Baseline L74I (Non-mixture) INSTI Mutation: 
 ▪ Present ▪ Not Present ○ Baseline Pre-specified INSTI Mutation (Excluding L74I Non-mixture): 
 ▪ Present ▪ Not Present ○ Baseline RPV RAM: 
 ▪ Present ▪ Not Present ○ Baseline NNRTI RAM (Excluding RPV RAM): 
 ▪ Present ▪ Not Present |
| EMA Subgroup Category 3: | |
| Additional subgroup/covariates for PK/PD efficacy analysis | 
PK/PD efficacy analysis will be performed for participants without prior exposure to CAB + RPV.
 
 ● Week 8 CAB/RPV Trough PK concentration (i.e. pre-dose PK concentration at nominal visit of Week 8) 
The above covariate will be dichotomized into two subgroup factors as follows:
 
 ○ \leq first Quartile vs $>$ first quartile, ○ \leq Median vs $>$ Median 
The concentration will also be treated as continuous variable in logistic regression modelling analysis (i.e. the concentration data will be \log_2 transformed in this analysis so that, for assessing the effect, one unit increase of the point estimate of \log_2 PK concentration is equivalent to 'doubling the concentration' in the original value).
 
 ● Length of First CAB/RPV Injection Needle (<2, ≥ 2 inches) |
| Additional subgroup/covariates for PK/PD safety analysis | 
Last CAB/RPV trough PK concentration
 
For the plot of Maximum Change from Baseline (CFB) in ALT/Total Bilirubin versus Last Trough CAB/RPV PK Concentrations, Last CAB/RPV Trough PK Concentration is the most recent trough PK concentration prior or equal to the date of the lab assessment with maximum CFB during the maintenance phase.
 
For the Plot of Maximum Toxicity Grades of Most Frequently Reported Study Drug ISR adverse events (AEs) versus Last Trough CAB/RPV PK Concentrations, Last CAB/RPV Trough PK Concentration is the most recent trough PK concentration prior or equal to the earliest onset date of the most frequently reported Study Drug ISR AE with maximum toxicity grade, during the maintenance phase. If a participant has no Study Drug ISR AE most commonly
 |

| Category | Covariates and / or Subgroups |
|--|--|
| | reported, then the last trough value during the maintenance phase will be used for the plot. |

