11.1. Overview of Planned Analyses

Table 6 provides an overview of the planned analyses with full details being presented in Appendix 15: List of Data Displays. All PK displays will be based on the PK Population, unless otherwise specified.

Table 6 Overview of Planned Pharmacokinetic / Pharmacodynamic Analyses

| | Stats Analysis | | | Summary | | Individual | |
|---|----------------|---|---|---------|---|------------|---|
| | T | F | L | T | F | F | L |
| CAB/RPV Week 8 concentrations by snapshot 'HIV-1 RNA \geq 50 c/mL' (Yes vs. No) at Week 48 for participants without prior exposure to CAB+RPV | | | | Y | Y | | |
| Analysis of snapshot 'HIV-1 RNA \geq 50 c/mL' at Week 48 by Week 8 trough concentration, and subgroup [1] – univariable analysis /multivariable analysis for participants without prior exposure to CAB+RPV | Y | | | | | | |
| Individual CAB/RPV concentration-time profiles for participants with snapshot 'HIV-1 RNA \geq 50 c/mL' at Week 48 or 96 or 152 | | | | | Y | | |
| Maximum change from baseline in ALT/Total Bilirubin versus last trough CAB/RPV concentrations for Week 48 and Week 152 analyses[2] | | | | | Y | | |
| Change from baseline in pre-dose QTcF versus CAB/RPV concentrations at Week 48 or 152 | | | | | Y | | |
| Maximum toxicity grades of most frequently reported study drug ISR AEs [3] versus last trough CAB/RPV PK concentrations for Week 48 analysis[2] | | | | | Y | | |

NOTES:

- T = Table, F = Figure, L = Listings, Y = Display generated.
- Stats Analysis = Represents TFL related to any formal statistical analyses (i.e. modelling) conducted.
- Summary = Represents TF related to any summaries (i.e. descriptive statistics) of the observed raw data.
- Individual = Represents FL related to any displays of individual participant observed raw data.

1. Refer to Section [11.2](#).
2. Display by rederived randomization strata, i.e. prior exposure to CAB+RPV (0, 1-24, >24 weeks) derived based on eCRF.
3. Most frequently reported study drug ISR AEs are those top 5 in incidence in either treatment arm (i.e. Q8W or Q4W arm).

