| NOTES: 
 The nominal Week 100 visit refers to the Week 100 visit per eCRF. Follow-up will be derived only for participants who permanently discontinued study treatment. 
[a] Urinalysis: All parameters provided by the central laboratory under the category of urinalysis, including Urine Albumin/Creatinine, Urine Creatinine, Urine pH, Urine Protein/Creatinine, Urine Erythrocytes, Urine Specific Gravity, Urine Leukocytes, Urine Retinol Binding Protein, Urine Phosphate, Urine Creatinine.
 
[b] Lipids: Cholesterol, HDL Cholesterol Direct, LDL Cholesterol Calculation, LDL Cholesterol Direct, Total Cholesterol/HDL Cholesterol Ratio, Triglycerides
 
[c] Analysis windows for parameters with sparse collection are noted.
 | | | |

Table 9 Assessment Windows for Extension Phase Data

| All Parameters except for where noted ^[d] | Target Study Day | Analysis Window | Analysis Timepoint |
|---|------------------|---|-------------------------|
| | 729 | (Study Day of Nominal Week 100 Visit + 1) ≤ Study Day ≤ 756 | Week 104 ^[a] |
| | 785 | 757 ≤ Study Day ≤ 812 | Week 112 |
| | 841 | 813 ≤ Study Day ≤ 868 | Week 120 |
| | 897 | 869 ≤ Study Day ≤ 924 | Week 128 |
| | 953 | 925 ≤ Study Day ≤ 980 | Week 136 |
| | 1009 | 981 ≤ Study Day ≤ 1036 | Week 144 |
| Urinalysis ^[b] , fasting glucose, lipids ^[c] , CD8, CD4/CD8 ratio, weight, vital signs, ECG | 1065 | 1037 ≤ Study Day ≤ 1106 | Week 152 |
| | | 1037 ≤ Study Day ≤ 1092 | |

| All Parameters except for where noted ^[d] | Target Study Day | Analysis Window | Analysis Timepoint |
|--|------------------|--|----------------------------|
| | 7*w + 1 | (7*w - 27) ≤ Study Day ≤ (7*w + 28) | Week w w = 160, 168,... |
| If a participant permanently discontinued study treatment: | | | |
| | | For participants on Q8W Arm: Date > max (Date of Last Dose of Oral Study Treatment (CAB+RPV or SOC Bridging) + 1, Date of Last Injection + 63) | Follow-up |
| | | For participants on Q4W Arm: Date > max (Date of Last Dose of Oral Study Treatment (CAB+RPV or SOC Bridging) + 1, Date of Last Injection + 35) | |

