15.3.5. Assessment Window for PK Concentration Data

15.3.5.1. Maintenance and Extension Phase Assessments

For PK concentration data at the withdrawal/unscheduled/LTFU Month 1 visits during the maintenance and extension phase (after assignment to study phase per [Table 18](#)), the visit will be slotted to the analysis visit per the following steps:

- Identify the ‘last nominal visit’ with the planned PK pre-dose assessment prior to the visit to be slotted during the same study phase
- Identify the nominal visit corresponding to the next planned pre-dose PK assessment visit (excluding visits with storage PK collection), that is subsequent to the ‘last nominal visit’ with PK pre-dose assessment during the same study phase. If the ‘last nominal visit’ during the maintenance phase does not exist, the first planned pre-dose PK assessment visit for the participant during the maintenance phase will be considered the nominal visit corresponding to the next planned pre-dose PK assessment. If the ‘last nominal visit’ during the extension phase does not exist, slot the PK assessment to the nominal visit of the next planned injection occurring on or after the date of the PK assessment during the extension phase.
- If the nominal visit corresponding to next planned pre-dose PK assessment visit is prior to/at Week 48 visit, the PK assessment at the unscheduled/withdrawal/LTFU Month 1 visit will be slotted to this nominal visit corresponding to next planned pre-dose PK assessment visit.
- Otherwise, the PK assessment at the unscheduled/withdrawal/LTFU Month 1 visit will be slotted to the earliest nominal visit from the following:
 - Nominal visit corresponding to the next planned pre-dose PK assessment visit
 - The nominal visit of the next planned injection occurring on or after the date of the PK assessment during the same study phase

If both the next planned pre-dose PK assessment visit and the next planned injection visit during the same study phase are not available, for example, withdrawal PK assessment taken after Week 96 for participants on Q8W arm, the PK assessment will be slotted to Week 100 visit.

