During the maintenance and extension phase, the planned nominal visits for PK Pre-dose are Week 4B, 8, 16, 24, 32, 40, 48, 96, 152 for Q4W arm; and are Day 1, Week 4B, 8, 16, 24, 32, 40, 48, 96, 152 for Q8W arm while Day 1 is required only for those transitioning from ATLAS on Q4W injections and Week 4B is required only for participants transitioning from oral SOC and requiring oral CAB+RPV lead-in. In addition, the participants on Q8W arm have planned nominal visits at Week 9 and 41 for 1-week post-dose.

For participants requiring oral CAB+RPV lead-in, the planned injection visits are Week 4B, Week 8, continuing every 4 weeks for Q4W arm and continuing every 8 weeks for Q8W arm. For participants not requiring oral CAB+RPV lead-in, the planned injection visits are every 4 weeks starting from Day 1 for Q4W arm and every 8 weeks starting from Day 1 for Q8W arm.

Example 1: If a participant on Q8W arm has the 'last nominal visit' (with PK pre-dose assessment) at Week 24 and then withdraws around Week 28, with the last injection at Week 24 and a Maintenance Phase PK assessment labelled at 'LTFU Month 1', This PK assessment labelled as 'LTFU Month 1' will be slotted to the subsequent planned nominal visit of Week 32.

Example 2: If a participant on Q4W arm has the 'last nominal visit' (with PK pre-dose assessment) at Week 48 and then have an unscheduled Maintenance Phase PK assessment around Week 74. This assessment will be slotted to the next planned injection visit, Week 76.

There will be no slotting for planned nominal visits (i.e. analysis visit =visit).

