15.15.6.8. Pharmacokinetic / Pharmacodynamic Figures

| Pharmacokinetic / Pharmacodynamic Figures | | | | | |
|---|-----------------|------------------------|---|---|-------------|
| No. in W152 | Population | IDSL / Example Shell | Title | Programming Notes | Deliverable |
| PK / PD Efficacy Analyses | | | | | |
| 5.1 | Pharmacokinetic | 207966/primary_15/F5.1 | Individual CAB Trough Concentration-time Profiles for Subjects with Snapshot 'HIV-1 RNA ≥ 50 c/mL' at Week 152 and Median, 5th & 95th Percentile of CAB Conc-Time Profiles for Other Subjects (Semi-Log) – Maintenance + Extension Phase | | W152 |
| 5.2 | Pharmacokinetic | 207966/primary_15/F5.2 | Individual RPV Trough Concentration-time Profiles for Subjects with Snapshot 'HIV-1 RNA ≥ 50 c/mL' at Week 152 and Median, 5th & 95th Percentile of RPV Conc-Time Profiles for Other Subjects (Semi-Log) – Maintenance + Extension Phase | | W152 |
| PK / PD Safety Analyses | | | | | |
| 5.3 | Pharmacokinetic | 207966/primary_02/F5.6 | Scatter Plot of Maximum Change from Baseline in ALT versus Last Trough CAB PK Concentrations by Strata and Treatment during the Maintenance and Extension Phase | Replace "Maintenance" with "Maintenance and Extension" in the first footnote. | W152 |
| 5.4 | Pharmacokinetic | 207966/primary_02/F5.7 | Scatter Plot of Maximum Change from Baseline in ALT versus Last Trough RPV PK Concentrations by Strata and Treatment during the Maintenance and Extension Phase | Replace "Maintenance" with "Maintenance and Extension" in the first footnote. | W152 |
| 5.5 | Pharmacokinetic | 207966/primary_02/F5.8 | Scatter Plot of Maximum Change from Baseline in Total Bilirubin versus Last Trough CAB PK Concentrations by Strata and Treatment during the Maintenance and Extension Phase | Replace "Maintenance" with "Maintenance and Extension" in the first footnote. | W152 |

| Pharmacokinetic / Pharmacodynamic Figures | | | | | |
|---|-----------------|-------------------------|---|---|-------------|
| No. in W152 | Population | IDSL / Example Shell | Title | Programming Notes | Deliverable |
| 5.6 | Pharmacokinetic | 207966/primary_02/F5.9 | Scatter Plot of Maximum Change from Baseline in Total Bilirubin versus Last Trough RPV PK Concentrations by Strata and Treatment during the Maintenance and Extension Phase | Replace "Maintenance" with "Maintenance and Extension" in the first footnote. | W152 |

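### In the Week 152 liver plots the last-trough rule has no age limit, so most planned lab visits after Week 48 are paired with a concentration more than 8 weeks old

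*SAP*

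**What the plan says.** Section 5.4.2, in the row on additional covariates for the PK/PD safety analysis, defines the exposure value for these plots as "the most recent trough PK concentration prior or equal to the date of the lab assessment with maximum CFB", and confines this to the maintenance phase. It gives no maximum age for that trough.

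Table 6 in Section 11.1 plans the display "Maximum change from baseline in ALT/Total Bilirubin versus last trough CAB/RPV concentrations for Week 48 and Week 152 analyses". In Section 15.15.6.8, Figures 5.3 to 5.6 carry it out for ALT and total bilirubin against CAB and RPV. The first is titled "Scatter Plot of Maximum Change from Baseline in ALT versus Last Trough CAB PK Concentrations by Strata and Treatment", and its title goes on to cover Maintenance and Extension. The programming note only widens the phase named in the footnote.

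On PK timing, Section 15.3.5.1 states that "planned nominal visits for PK Pre-dose are Week 4B, 8, 16, 24, 32, 40, 48, 96, 152 for Q4W arm". The Q8W list is the same with Day 1 added. When that section looks for the next planned pre-dose PK visit, it does so "excluding visits with storage PK collection". Lab timing comes from Tables 8 and 9 in Section 15.3.2, where analysis visits stay 8-weekly through Week 152; the Week 144 window, for example, is "981 ≤ Study Day ≤ 1036".

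**The concern.** The rule is keyed to the date of the peak lab value, so it is meant to pick up exposure near that date. Up to Week 48 it can do so, because planned troughs and labs run on the same 8-weekly grid. After Week 48 planned troughs become sparse and the rule still returns a value, however old.

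Much can change in the gap. Section 15.6.4 itself provides for late and missed injections, oral bridging and reloading. Section 15.6.5 also keeps PK drawn for a liver event out of the figures, so the sample closest to the event of interest cannot fill the gap.

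Hepatotoxicity is an adverse event of special interest (Section 8.2), and relating concentrations to adverse events is a stated exploratory objective (Section 2.2). A stale exposure value tends to blur any such relation. A flat Week 152 plot could then be read as reassurance, with nothing in the definition or the display notes to warn that many of the pairings may be old.

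The wording is also inconsistent: Section 5.4.2 confines the definition to the maintenance phase, while Figures 5.3 to 5.6 run through the extension phase.

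**Working it through.** The SAP states no figure for the age of the paired trough, so there is none to reproduce.

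**Inputs**
- Planned analysed troughs P, in weeks: 8, 16, 24, 32, 40, 48, 96, 152 (Section 15.3.5.1). Week 4B and Day 1 are left out because they do not affect the result after Week 48.
- Planned lab visits L after Week 48: 56, 64, 72, 80, 88, 96, 104, 112, 120, 128, 136, 144, 152 (Section 15.3.2, Tables 8 and 9), which is 13 visits.

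**Formula**

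lag(L) = L − the largest P with P ≤ L. Equality counts, because the rule accepts a trough on the same date as the lab.

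**Results, in weeks**

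| Lab visits | Lag at each visit | Sum | Longest |
|---|---|---|---|
| 8 to 48 | 0 at every visit | 0 | 0 |
| 56, 64, 72, 80, 88, 96 | 8, 16, 24, 32, 40, 0 | 120 | 40 (Week 88 lab, Week 48 trough) |
| 104, 112, 120, 128, 136, 144, 152 | 8, 16, 24, 32, 40, 48, 0 | 168 | 48 (Week 144 lab, Week 96 trough) |

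- Mean lag over the 13 visits: (120 + 168) / 13 = 288 / 13 = 22.2 weeks.
- Visits with a trough more than 8 weeks old: 4 (Weeks 64 to 88) + 5 (Weeks 112 to 144) = 9 of 13.

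**Departures from the planned schedule**
- Week 152 PK missed, which the note to Table 4.1 in Section 15.15.6.6 foresees: the Week 152 lab pairs with Week 96, and 152 − 96 = 56 weeks.
- Unscheduled lab one day before Week 152: study day 1064 − study day 673 = 391 days, or 55.9 weeks.
- Week 96 PK missed: the Week 144 lab pairs with Week 48, and 144 − 48 = 96 weeks.
- Withdrawal and unscheduled samples (Sections 15.3.5.1 and 15.6.5) work the other way and may shorten some lags. They are not systematic, and their number is not known.

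If the maintenance-phase wording of Section 5.4.2 is read literally, the longest planned lag is 40 weeks. The 48 weeks arises because Section 15.15.6.8 extends the period.

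**The case against.** The best defence is that the plan calls the variable a last trough, not a concurrent one. Its PK/PD efficacy analysis deliberately relates the Week 8 trough to a Week 48 outcome, so an earlier trough can serve as a participant-level measure of exposure. Steady state is examined separately, all concentrations are listed, and these figures carry no model, test or decision rule.

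Part of this stands. The consequences are limited to descriptive figures, and an old trough is a noisy measure rather than a wrong one. The participant-level argument does not fit, however. A rule that picks the trough by the date of the peak lab is a time-matching rule, whereas the efficacy analysis fixes one visit for everyone. The steady-state analysis in Section 9.3 covers only the Q8W arm, over Weeks 16 to 48. In the same display set, the QTcF plots (Figures 5.7 and 5.8) take change and trough at the same visit.

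A reader might infer from the Week 96 to Week 152 gap that pairings 56 weeks old are routine. The documents do not support that: with 8-weekly labs and complete PK, the Week 152 lab pairs with the Week 152 trough and the longest lag is 48 weeks. Reaching 56 weeks takes a missed Week 152 sample, and coming close to it takes an unscheduled lab just before that visit. Nor is 56 weeks a ceiling, as the missed Week 96 case shows.

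**Conclusion.** The concern holds for Figures 5.3 to 5.6 of the Week 152 analysis. On the planned schedule, 9 of 13 lab visits after Week 48 take a trough more than 8 weeks old, with a mean lag over the 13 of about 22 weeks and a longest lag of 40 weeks before Week 96 and 48 weeks after it. The same rule works at planned visits from Week 8 to Week 48.

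This rests on two assumptions: that labs follow the 8-weekly analysis windows, and that planned PK samples are taken and analysed as Section 15.3.5.1 lists them. How many participants reach their maximum change after Week 48 is unknown, so the share of plotted points affected cannot be stated. It would go too far to conclude that the trial's liver safety assessment is unsound. Maximum liver values are also shown without any PK pairing in Figures 3.7 and 3.8 (Section 15.15.6.5), and the primary analysis is untouched.

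**What to change.** For the Week 152 figures:

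1. Add a version that pairs each ALT or bilirubin change with the trough from the same visit, and plots the maximum change among those visits. Use the same planned PK visits in both arms: Weeks 8 to 48, then 96 and 152. Week 4B is best left out, since in the Q8W arm it is planned only for participants with an oral lead-in.
2. Keep the overall-maximum version, flag points whose trough is older than one dosing interval, and report the number flagged by arm. Because the interval is 4 weeks for Q4W and 8 weeks for Q8W, planned visits alone would give 11 and 9 flagged of 13, so the two counts should not be compared directly.
3. Align the maintenance-phase wording in Section 5.4.2 with the Maintenance and Extension period in Section 15.15.6.8.

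An age limit taken from the on-treatment windows (35 days for Q4W, 63 for Q8W) is not a good substitute for the same-visit rule. A lag of 8 weeks is 56 days, so Q8W would keep four planned visits after Week 48 (56, 96, 104, 152) and Q4W only two (96, 152). A maximum over more visits tends to be larger, which would distort a display by treatment.

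The cost is SAP wording and reprogramming of four descriptive figures. The paired version omits maxima that fall between PK visits. Those stay in the flagged version and in Figures 3.7 and 3.8. The hepatobiliary listings would not cover all of them, since they include only participants who meet the lab criteria.

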5.5. Multiple Comparisons and Multiplicity

5.5.1. Primary Comparison of Interest

The primary analysis will be based on the ITT-E population. The primary comparison will be made at a one-sided 2.5% level of significance. Treatment with Q8W will be declared non-inferior to Q4W if the upper end of a two-sided 95% confidence interval for the difference between the two groups (Q8W – Q4W) in the proportion of participants with HIV-1 RNA ≥ 50 c/mL at Week 48 (defined by the US FDA snapshot algorithm) lies below 4%.

The primary comparison of interest is the comparison between Q8W (CAB LA + RPV LA Q8W) and Q4W (CAB LA + RPV LA Q4W) for the primary endpoint in the ITT-E population. This analysis will be adjusted for by the re-derived randomization strata based on eCRF data.

5.5.2. Other Comparisons of Interest

If the primary comparison of interest (Section 5.5.1) using the ITT-E population demonstrates non-inferiority of Q8W compared to Q4W then the following key secondary comparisons will be tested:

- Treatment with Q8W will be declared non-inferior to Q4W with respect to the proportion of participants with HIV-1 RNA < 50 c/mL at Week 48 (defined by the US FDA snapshot algorithm) if the lower end of a two-sided 95% confidence interval for the difference between in rates (Q8W – Q4W) lies above -10% using the ITT-E population

- Superiority of Q8W compared to Q4W with respect to change from baseline HIVTSQs total score at Week 48 using the ITT-E population and a two-sided 5% level of significance. Refer to Section 12.5.1 for details.

For the primary endpoint treatment comparison at Week 48, no multiple comparison adjustment is necessary for testing non-inferiority followed by superiority (conditional on achieving a significant test for non-inferiority) since testing follows a pre-specified sequence of hypothesis such that if the first hypothesis tested is not significant, all subsequent tests will not be performed. This fixed sequence procedure controls the type I error rate at the nominal level. The primary endpoint treatment comparison at Week 48 will also be performed using the PP population and the results will be compared for consistency with the results from the ITT-E population.

In addition to the primary and the key secondary comparisons, the comparisons between two treatment arms for ACCEPT (general acceptance score), PIN (Domain scores (Bother of ISRs, Leg movement, Sleep, and Acceptance) and Individual Items Scores (Anxiety before, Pain, Satisfaction, Anxiety After, Willingness)), HAT-QoL (Life satisfaction, HIV medications, disclosure worries) and HIVTSQc (Treatment Satisfaction score) at timepoints through Week 48 will also be performed as supportive analyses.

Lastly, for the IDMC interim analyses, since the statistical stopping guidelines will not result in early stopping for positive efficacy findings, these interim treatment comparisons will not inflate the Type I error rate for the primary treatment comparison.

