$$P_k = \frac{n_k^2 y_k - m_k^2 x_k + n_k m_k (m_k - n_k) / 2}{N_k^2}$$

$$Q_k = \frac{x_k (m_k - y_k) / N_k + y_k (n_k - x_k) / N_k}{2}$$

with x_k and y_k corresponding to the number of participants with Plasma HIV-1 RNA ≥ 50 c/mL at Week 48 per FDA Snapshot for Q8W and Q4W, respectively, for the k th stratum.

Model Results Presentation

- Adjusted CMH estimate of the difference in the proportion of subjects with Plasma HIV-1 ≥ 50 c/mL between each treatment group (Q8W – Q4W) and corresponding 95% confidence interval.
- Non-inferiority will be concluded if the upper bound of the two-sided 95% confidence interval for the CMH adjusted treatment difference (Q8W – Q4W) is less than 4%.
- If this analysis shows non-inferiority, then a superiority hypothesis will be tested at the two-sided 5% level of significance. Superiority favoring Q8W will be declared if the upper bound of the confidence interval is below 0% for the ITT-E population analysis. If superiority is declared, the p-value for superiority will also be calculated.

Subgroup Analyses

- Treatment Heterogeneity across rederived randomization strata [prior exposure to CAB+RPV (0 weeks, 1-24 weeks, >24 weeks)]:
 - The weighted least squares chi-squared statistic [Fleiss, 1981] will be used to test for one-way homogeneity across the levels of each categorical variable, with each categorical variable considered separately.
 - Following Lui and Kelly [Lui, 2000] $\frac{1}{2}$ will be added to each cell in any strata for which the stratum-specific rate estimates of either f_{Q8W} or f_{Q4W} are zero or one, and tests will be one-sided.
 - Any heterogeneity found to be statistically significant will be explored and if necessary results will be reported for each level of the categorical variable. Investigation of heterogeneity will be confined to the primary endpoint. Tests of homogeneity will be assessed at the one-sided 10% level of significance.
- Stratum-specific analyses for two groups of participants: (Group 1) those currently receiving Standard of Care antiretroviral therapy at Baseline (i.e. no prior exposure to CAB+RPV), (Group 2) those receiving Q4W CAB LA + RPV LA therapy in the ongoing ATLAS study (i.e. have prior exposure to CAB+RPV). For each stratum (Group 1 and Group 2), the following will be presented:
 - Proportion of subjects with plasma HIV-1 RNA ≥ 50 c/mL at Week 48 by treatment group.
 - Unadjusted difference in proportions between treatment groups and corresponding two-sided 95% CI.

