| 
 The analysis for HIVTSQs, ACCEPT and HAT-QoL will be performed for subjects with and without prior exposure to CAB+RPV separately. 
 For subjects without prior exposure to CAB+RPV, an analysis of covariance (ANCOVA) model will be used at each visit during the maintenance phase with covariates: treatment, age (<50, ≥ 50 years old), sex at birth, race (i.e. white, non-white) and baseline score value for other endpoints (as a continuous variable). For subjects with prior exposure to CAB+RPV, an analysis of covariance (ANCOVA) model will be used at each visit during the maintenance phase with covariates: treatment, age (<50, ≥ 50 years old), prior exposure to CAB+RPV (i.e. 1 to 24 weeks, >24 weeks), sex at birth, race (i.e. white, non-white) and baseline score value (as a continuous variable). For PIN, an analysis of covariance (ANCOVA) model will be used at each visit during the maintenance phase with covariates: treatment, age (<50, ≥ 50 years old), prior exposure to CAB+RPV (i.e. 0 weeks, 1 to 24 weeks, >24 weeks), sex at birth, race (i.e. white, non-white), and Week 8 score value (as a continuous variable). Adjusted point estimates will be derived as LSMEANS using the observed margins (OM) option within PROC MIXED in SAS. The superiority testing of Q8W compared to Q4W with respect to change from baseline in HIVTSQs total score at Week 48 will be performed using the fixed sequence procedure to control for the type I error rate at the nominal level of 5%. If the superiority testing within subjects without prior exposure to CAB+RPV demonstrates Q8W is superior to Q4W in change from baseline in HIVTSQs total score at Week 48 at two-sided 5% level of significance, the superiority testing at the same level of significance (i.e. two-sided 5%) within subjects with prior exposure to CAB+RPV will be followed. No adjustment for multiplicity will be applied for other tests as they will be considered supportive. Interactions between treatment and each of the covariates will not be assessed unless the exploratory subgroup analyses on the primary endpoint highlights significant interactions. In this situation, the interaction(s) of interest will be assessed and, if necessary, results will be reported in the clinical study report. Interactions between treatment and the baseline score will be investigated but not included in the model. If interactions are found to be significant ($p < 0.10$), results may be presented separately by subgroup. | |

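### Three formal tests open at full level once primary non-inferiority is met, and nothing controls type I error across them

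*SAP*

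**What the plan says.** Section 5.5.1 sets the gate: "The primary comparison will be made at a one-sided 2.5% level of significance", judged on the two-sided 95% confidence interval against a 4% margin.

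Section 5.5.2 then says that if the gate is passed, "then the following key secondary comparisons will be tested", and lists two:

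- **Branch A**, non-inferiority on HIV-1 RNA <50 c/mL at Week 48, met "if the lower end of a two-sided 95% confidence interval for the difference between in rates (Q8W – Q4W) lies above -10" per cent.
- **Branch B**, superiority of Q8W on change from baseline in HIVTSQs total score at Week 48, "using the ITT-E population and a two-sided 5% level of significance". Section 12.5.1 runs this as two tests, first in participants without prior CAB+RPV exposure and then in those with it, and says it "will be performed using the fixed sequence procedure to control for the type I error rate at the nominal level of 5" per cent.

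**Branch C** comes from Section 7.1.5.1: "If this analysis shows non-inferiority, then a superiority hypothesis will be tested at the two-sided 5% level of significance". Section 5.5.2 covers this step as well. It explains that non-inferiority followed by superiority on the primary endpoint needs no adjustment, and adds: "This fixed sequence procedure controls the type I error rate at the nominal level".

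Section 5.5.2 separates these tests from the ACCEPT, PIN, HAT-QoL and HIVTSQc comparisons, which it calls supportive.

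**The concern.** Branches A, B and C share one gate and nothing else. No section says that failing one stops another, and none divides the level among them. A fixed sequence protects the error rate only because each test waits for the one before it. Two valid sequences and a further test, run side by side from the same starting point, do not form one sequence.

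The SAP treats these as claims: superiority is to be declared, and non-inferiority concluded. A report could therefore present an HIVTSQs result or a primary-endpoint superiority result as fully type I error controlled, when the plan provides control only inside each chain.

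**Working it through.** **Inputs from the SAP**

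- Gate: one-sided 2.5% (5.5.1).
- A: two-sided 95% interval, so one-sided 2.5% (5.5.2).
- B: two-sided 5%, so 2.5% for a false claim in favour of Q8W (5.5.2, 12.5.1). The second HIVTSQs test opens only after the first succeeds, so the branch as a whole stays at 2.5%.
- C: superiority when the upper 95% bound is below 0%, so one-sided 2.5% (7.1.5.1).
- Size: 1020 randomized 1:1, 510 per arm (Sections 1 and 2.3).

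**Inputs assumed, not in the SAP**

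- HIVTSQs independent of the virologic outcome.
- For the simulation, a rate of HIV-1 RNA ≥50 c/mL of 2% or 4% in both arms.

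**Step 1: the SAP's own figure.** A 95% interval bound uses z = 1.96, and 1 − Φ(1.96) = 0.0250. Non-inferiority then superiority on one endpoint uses nested hypotheses and one interval, so that chain stays at 2.5% one-sided. The SAP's statement about it is reproduced.

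**Step 2: arms truly equal on failure rate and satisfaction.** Q8W is then truly non-inferior on <50 c/mL as well, provided missing data are also alike, so A cannot produce a false claim. B and C can:

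- Independent: 1 − 0.975² = 0.0494.
- Any dependence: at most 2 × 0.025 = 0.05, and never below the 0.025 of one branch alone.

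**Step 3: corner case.** Q8W sits exactly at the −10% margin on <50 c/mL, with failure rate and satisfaction still equal:

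- Independent: 1 − 0.975³ = 0.0731.
- Any dependence: at most 3 × 0.025 = 0.075.

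**Step 4: simulation.** 400,000 trials, 510 per arm, three-category snapshot outcome, unstratified Wald 95% intervals, one independent normal HIVTSQs statistic. Errors count claims in favour of Q8W.

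| True state | As written | One fixed order |
|---|---|---|
| Arms equal (2% failure, 5% no data in both) | 0.0491 | 0.0248 |
| Corner case, 2% failure, no data 15% Q8W v 5% Q4W | 0.0717 | 0.0263 |
| Corner case, 4% failure, no data 15% Q8W v 5% Q4W | 0.0678 | 0.0265 |

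The fixed order simulated was primary non-inferiority, then A, then B (as a single test), then C. The small excess over 0.025 comes from the Wald interval.

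**Step 5: effect on the primary test.** With Q8W placed at the 4% margin (6% v 2%), the overall error was 0.0316 as written. That equals the probability of passing the gate, so the later tests add nothing to it. The excess over 0.025 belongs to the simple Wald interval used here, not to the stratified interval that the SAP specifies.

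**The case against.** The best defence is that the SAP does not claim what it fails to deliver. A reader might infer that its fixed-sequence sentences are false. They are not. The one in Section 5.5.2 is confined to non-inferiority followed by superiority on the primary endpoint, and the one in Section 12.5.1 to the two HIVTSQs tests. Both hold within those limits. The defect is absent control across branches, not a wrong statement about either chain.

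It could also be said that the order of the two bullets in Section 5.5.2 implies a sequence. The text does not support that: both are conditioned on the primary comparison alone. Where the SAP wants one test to wait for another it says so, and Section 7.2.5.1 does not make the <50 c/mL result a condition for HIVTSQs. Even if the bullets were ordered, primary-endpoint superiority would have no place relative to them.

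A fair point on size stands. If Q8W is truly non-inferior on <50 c/mL, the two comparisons named as key secondary carry only the HIVTSQs error of 2.5% between them. The rise to 4.9% comes from HIVTSQs alongside primary-endpoint superiority.

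A fair point on timing also stands. Section 5.4.2 describes baseline genotypic data as arriving after the Week 48 analysis data cut, and Section 1.1 shows that this amendment was written for the sub-study. An order written now cannot be called prespecified for Week 48.

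**Conclusion.** The point holds as a gap in control across branches, and it is a should-fix. Following the plan as written gives about 4.9% one-sided for at least one false superiority claim for Q8W when the arms are truly equal, roughly twice the nominal 2.5%. This assumes independence between HIVTSQs and the virologic outcome. Perfect positive dependence would bring it down to 2.5%, and no dependence can take it above 5%.

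Two stronger readings should be resisted. A reader might infer that the primary non-inferiority conclusion is compromised. It is not, because every branch opens only after it and adds nothing to its error. A reader might also take about 7% as the working error rate. That needs Q8W to be 10 points worse on <50 c/mL while still meeting the 4% margin on ≥50 c/mL, which in the simulation took a 10-point imbalance in missing virologic data. It marks the edge of what is possible and is not an expected value.

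**What to change.** In Section 5.5.2, with cross-references from 7.1.5.1 and 12.5.1, place all these tests in one stated procedure. Any of the following would do:

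- **A single order**, stopping at the first test that fails. One example is primary non-inferiority, non-inferiority on <50 c/mL, HIVTSQs without prior exposure, HIVTSQs with prior exposure, primary-endpoint superiority.
- **A Holm or other alpha split** across the three branches after the gate. An equal Bonferroni split gives 0.025/3 = 0.0083 one-sided each.
- **A declaration** of which tests lie outside family-wise control, with those results reported as descriptive.

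Whichever is chosen, Section 5.5.2 should show HIVTSQs as the two tests that Section 12.5.1 runs, not as one.

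For Week 48, do not present a new order as prespecified. State which claims were type I error controlled, and label the HIVTSQs and primary-superiority results as not jointly controlled.

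The cost is aligned wording in three sections and some loss for later tests. Under a single order they depend on earlier ones: in the example, primary-endpoint superiority would wait on both HIVTSQs tests, whereas now it follows directly from non-inferiority. Under a split, each branch loses power.
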